## Post-Authorization Safety Study (PASS) Information

Acronym/Title	HEM-POWR: Observational Study Evaluating Effectiveness and Safety of Real-World Treatment with Damoctocog alfa pegol in Previously Treated Patients with Hemophilia A
Protocol version and date	v 1.1, 18 MAR 2019
IMPACT study number	20002
Study type/Study phase	Observational, post-approval  non-PASS  PASS Joint PASS:  YES  NO
EU PAS register number	Study not yet registered
Active substance	ATC code: B02BD02/Hematological/Damoctocog alfa pegol
Medicinal product	Damoctocog alfa pegol
Product reference	EU/1/18/1324/001 Jivi 250 IU; EU/1/18/1324/002 Jivi 500 IU; EU/1/18/1324/003 Jivi 1000 IU; EU/1/18/1324/004 Jivi 2000 IU; EU/1/18/1324/005 Jivi 3000 IU
Procedure number	EMA/H/C/004054
Study Initiator and Funder	Bayer Consumer Care AG, Basel, Switzerland
Research question and objectives	The objectives of this study are to assess the effectiveness and long term safety of prophylaxis with damoctocog alfa pegol in the real-world setting through the collection of total bleeding events and analysis of the annualized bleeding rate (ABR) in the different prophylaxis regimens (following approved local label or any other regimen prescribed by the physician as part of normal clinical practice) in patients with hemophilia A. The analyses will be stratified, based on severity of hemophilia, severity of patient bleeding profile, disease characteristics, prophylaxis regimen, age, and time on treatment (i.e., damoctocog alfa pegol-naive or not).  In addition, the study will capture patterns of switching in

	
damoctocog alfa pegol dose and dosing regimen, reasons for choice of treatment regimen, damoctocog alfa pegol consumption, adverse events, pharmacokinetics (if part of routine practice), as well as patient treatment satisfaction, work productivity and activity impairment.
 
Patients participating in HEMPOWR will be offered to enroll into a sub-study arm evaluating activity with an activity tracking device (ActiGraph; patient will be blinded to the activity tracking device values). The objective of the sub-study is to investigate relationship between patient daily regular activity and efficacy parameters collected from HEM-POWR.
 
Enrollment into HEM-POWR is not influenced by the patient's decision whether to participate in the sub-study or not. Participation in the sub-study is fully voluntary and will not impact the main objectives or data collected in HEM-POWR. Details of the sub-study, including the analysis of the activity data will be described in a separate sub-study protocol as a part of the main study.

Countries of study
	
The study is planned to be conducted in Austria Belgium/Luxemburg, Brazil, Canada, China, Colombia, Finland, France, Germany, Greece, Italy, Japan, Kuwait, Mexico, Netherlands, Russia, Saudi Arabia, Scandinavia (Denmark, Norway and Sweden), Slovenia, Spain, Switzerland, Taiwan, UAE and USA. The study may also be conducted in other countries not currently listed.

Author
	
PPD [redacted]                  [name]

## 2. List of abbreviations

ABR	Annualized bleeding rate
AE	Adverse Event
AR	Adverse reaction
ATC	Anatomical Therapeutic Chemical (Classification System)
BDD-rFVIII	B-domain–deleted recombinant factor VIII
CFR	Code of Federal Regulations
CI	Confidence interval
CIQ	Classroom impairment questions
CRO	Contract Research Organization
DMP	Data Management Plan
eCRF	Electronic Case Report Form
EDC	Electronic Data Capture
EFPIA	European Federation of Pharmaceutical Industries and Associations
EMA	European Medicine Agency
ENCePP	European Network of Centers in Pharmacoepidemiology and Pharmacovigilance
EU	European Union
FAS	Full analysis set
FDA	US Food and Drug Administration
FVIII	Factor VIII
GPP	Good Publication Practice
GVP	Good Pharmacovigilance Practice
HEAD-US	Hemophilia Early Arthropathy Detection with Ultrasound
Hemo-QoL-A	Hemophilia Quality of Life Measure for adults
Hemo-QoL-SF	Hemophilia Quality of Life short form for children
Hemo-SAT A	Hemophilia Treatment Satisfaction Questionnaire for adults
HJHS	Hemophilia Joint Health Score
HS	Hemophilia Specific
ICH	International Council for Harmonisation
IEC	Independent Ethics Committee
IRB	Institutional Review Board
ITI	Immune tolerance induction

IU	International units
MAH	Marketing Authorization Holder
MedDRA	Medical Dictionary for Regulatory Activities
MRP	Medical Review Plan
OS	Observational Study
PAS	Post-Authorization Study
PASS	Post-Authorization Safety Study
PEG	Polyethylene glycol
PK	Pharmacokinetic
PRO	Patient-reported outcome
PT	Preferred Term
PTP	Previously treated patient
QPPV	Qualified Person Responsible For Pharmacovigilance
QRP	Quality Review Plan
rFVIII	Recombinant factor VIII
SAE	Serious Adverse Event
SAF	Safety analysis set
SAP	Statistical Analysis Plan
SD	Standard deviation
SOC	System Organ Class
STROBE	Strengthening the Reporting of Observational Studies in Epidemiology
TEAE	Treatment-Emergent Adverse Event
WPAI	Work Productivity and Activity Impairment Scale

### 3.2 Collaborators/Committees

Contact details on the coordinating and/or principal investigators, co-investigators and other site personnel for each country and site participating in the study are listed in a stand-alone document (see [Table 6](#)) which is available upon request.

Information on the Steering/Publication Committee Members and the respective Charters are kept as stand-alone documents (see [Table 6](#)) which are available upon request.

Administrative changes of responsible persons and/or the composition of the committees will be documented by updating the respective lists, but do not require formal protocol amendments.

#### 4. Abstract

Acronym/Title	HEM-POWR: Observational Study Evaluating Effectiveness and Safety of Real-World Treatment with Damoctocog alfa pegol in Previously Treated Patients with Hemophilia A
Protocol version and date	v 1.1, 18 MAR 2019
IMPACT study number	20002
Study type/Study phase	Observational, Post-approval  non-PASS  PASS Joint PASS:  YES  NO
Author	PPD [REDACTED]
Rationale and background	
Hemophilia A is an X-linked, inherited, genetic bleeding disorder characterized by deficiency of clotting factor VIII (FVIII). Hemophilia A comprises approximately 80% of all hemophilia cases, with an annual incidence of approximately 1 in 5,000 live male inhabitants. All races and economic groups are affected equally. Prevalence estimates vary by country, ranging between 5 and 21 cases per 100,000 male inhabitants.
 
Damoctocog alfa pegol is intended for prophylaxis and treatment of bleeds in previously treated patients (PTPs) with hemophilia A aged <math>\geq 12</math> years, with a predictable weekly dose that allows for the treatment regimen to be tailored to individual patient needs. An enhanced pharmacokinetic (PK) profile enables a potentially decreased dosing frequency compared with unmodified recombinant clotting FVIII. Efficacy and safety of prophylaxis dosing with damoctocog alfa pegol was demonstrated in 2 phase II/III clinical studies in adult, adolescent, and pediatric (<12 years of age) PTPs with severe hemophilia A.
 
The aim of the proposed study is to characterize in a real-world setting the effectiveness and long term safety of damoctocog alfa pegol drug usage. These results can be used to educate patients, payors and providers about real-world prophylaxis dosing regimens with damoctocog alfa pegol.
 
Patients participating in HEM-POWR will be offered to enroll into a sub-study arm evaluating activity with an activity tracking device (type of Actigraph or similar; patient will be

	
blinded to the activity tracking device values). The objective of the sub-study is to investigate relationship between patient daily regular activity and efficacy parameters collected from HEM-POWR.
 
Enrollment into HEM-POWR is not influenced by the patient’s decision whether to participate in the sub-study or not. Participation in the sub-study is fully voluntary and will not impact the main objectives or data collected in HEM-POWR. Details of the sub-study, including the analysis of the activity data will be described in a separate sub-study protocol as a part of the main study.

Research question and objectives
	
The primary objective in this study is:
 
 
• To assess the effectiveness of prophylaxis with damoctocog alfa pegol in the real-world setting through the collection of total bleeding events and analysis of annualized bleeding rate (ABR) in the different prophylaxis regimens (following approved local label) in patients with hemophilia A.
 
 
The secondary objectives in this study are to:
 
 
• Assess the long term safety of prophylaxis with damoctocog alfa pegol in the real-world setting through the collection and analysis of adverse events (AEs) of special interest (hypersensitivity reactions, loss of drug effect, renal impairment, neurocognitive disorders, and inhibitor development), AEs, serious adverse events (SAEs), and adverse reactions (ARs).
 
• Evaluate joint health (Hemophilia Joint Health Score [HJHS]).
 
• Collect information on affected joints at baseline and in the study.
 
• Assess hemostasis during surgeries during the study.
 
• Collect and evaluate patient-reported outcomes such as Hemophilia Treatment Satisfaction Questionnaire for adults (Hemo-SAT A), Hemophilia Quality of Life Measure for adults (Hemo-QoL-A), Hemophilia Quality of Life short form for children (Hemo-QoL-SF) and Work Productivity and Activity Impairment Scale (WPAI [+ CIQ: HS]).
 

Study design
	
Multinational, open-label, prospective, non-interventional, multicenter, cohort study. Each patient enrolled will be followed for 36 months (with the potential for further extension).


Population
	
Previously treated patients with hemophilia A receiving damoctocog alfa pegol with any kind of treatment modality (on-demand, prophylaxis, or intermittent prophylaxis), will be eligible to be enrolled into the study.

Variables
	
The variables for primary endpoint are:
 
 
• Annualized number of reported total bleeds.
 
• Severity of hemophilia
 
• Severity of patient bleeding profile
 
• Prophylaxis regimen
 
• Time on treatment (i.e., damoctocog alfa pegolnaive- or not)
 
• Disease characteristics
 
• Age.
 
 
The variables for secondary endpoints are:
 
 
• Occurrence, duration, treatment, severity, and outcome of AEs, SAEs, and ARs (including AEs of special interest [hypersensitivity reactions, loss of drug effect, renal impairment, neurocognitive disorders, and inhibitor development]).
 
• Number of reported total, spontaneous, joint, and trauma bleeds.
 
• Retrospective and prospective location and number of affected joints.
 
• Joint health measured by HJHS.
 
• Newly affected joints (number and location).
 
• Reported bleeds (number, type, location) during study and to 12 months prior to start of therapy with damoctocog alfa pegol.
 
• Number of infusions and FVIII consumption to achieve hemostasis during surgery
 
• Treatment satisfaction measured by Hemo-SAT A and Hemo-QoL (A and SF).
 
• Work productivity and activity impairment measured by WPAI [+ CIQ: HS].
 

Data sources
	
Historic data are based on medical records or on information provided by the patient during routine clinical visits. Treatment-related data are documented during visits that take place in routine practice. The patient documents bleeding events and all other events that require infusions in a patient infusion diary.
 
Validated patient questionnaires (Hemo-SAT A, Hemo-QoL [A and SF] and WPAI [+ CIQ: HS]) are used as sources for the

	
patient assessment on satisfaction and treatment adherence. The HJHS is used as source for joint health status. The HEAD-US score is used as source for joint health status of patients with hemophilic arthropathy.
								
Study size	The study aims to enroll at least 200 patients.								
Data analysis	
Statistical analyses will be of an explorative and descriptive nature. The study is not aimed to confirm or reject predefined hypotheses; hence no formal hypothesis testing will be performed.
 
All variables will be analyzed descriptively with appropriate statistical methods: categorical variables by frequency tables (absolute and relative frequencies) and continuous variables by sample statistics (i.e., mean, standard deviation, minimum, median, quartiles, and maximum). Continuous variables will be described by absolute value and as change from baseline per analysis time point, if applicable.
 
It is planned to have an annual interim analysis of baseline characteristics starting 1 year after the First Patient First Visit, and further annual analyses are planned on prospective treatment outcomes.
 
For the primary analysis summary statistics of the number of total reported bleeds will be presented. ABRs will be calculated as the number of bleeding events divided by the length (in years) of the treatment regimen. ABRs will be characterized using descriptive statistics by calculating mean (<math>\pm</math> standard deviation), median, minimum, and maximum.
								
Milestones	
 
 First patient first visit:	Q2 2019	
 
 Last patient first visit:	Q2 2022	
 
 Last patient last visit:	Q2 2025	
 
 Final report:	Q1 2026	
 
	First patient first visit:	Q2 2019	Last patient first visit:	Q2 2022	Last patient last visit:	Q2 2025	Final report:	Q1 2026
First patient first visit:	Q2 2019								
Last patient first visit:	Q2 2022								
Last patient last visit:	Q2 2025								
Final report:	Q1 2026								

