## 9. Research methods

### 9.1 Study design

This is a multinational, open-label, prospective, non-interventional, multicenter, cohort study of PTPs with hemophilia A receiving damoctocog alfa pegol with any kind of treatment modality (on-demand, prophylaxis, or intermittent prophylaxis). The study is planned to be conducted in multiple countries depending on timing of regulatory approval and national reimbursement access.

Prospective data will include prophylaxis regimen effectiveness measured by the number of ABR (reported in patient infusion diaries or documented by physicians, if patient infusion diary is not available), drug usage (IU/kg/infusion, IU/kg/year, and IU/kg/event), regimens used, patient-reported outcome (PRO) measurements (where applicable), such as validated, disease-specific and generic quality of life questionnaires and treatment satisfaction; as well as PK parameters (when available), joint outcomes (HJHS), and safety including AEs of special interest (hypersensitivity reactions, loss of drug effect, renal impairment, neurocognitive disorders, and inhibitor development) and drug-related ARs in standard clinical practice. Retrospective data will include documentation of previous therapy, lifetime duration on prophylaxis, medical condition, PK parameters (when available), and bleeds up to 12 months prior to use of damoctocog alfa pegol, in order to allow a stratification of patients by patient bleeding profile and disease characteristics (See Section 9.3.7).

Patients/legal representatives and physicians can choose from different prophylaxis regimens with damoctocog alfa pegol following approved local labels or any other regimen prescribed by the physician as part of normal clinical practice. Patients/legal representatives and physicians can choose to change the dosing regimen based on the patient's response to treatment at any time. A reason for the dose and/or frequency change should be documented.

The patients planned observation period will be 36 months (with the potential for further extension), for the collection of long-term safety data and continuous prospective monitoring of joint health status over time.

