**Lost to follow-up**

A patient is regarded as ‘Lost to follow-up’ in case no further information can be expected from the patient at a given point in time.

In case no information was obtained from a patient within 24 month since the last data collection time point the site personnel is requested to apply due diligence – within the applicable legal limits – to contact patients to ascertain the reason. In case no information can be retrieved, the site should confirm that the patient is lost to follow-up and document the end of observation.

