### **Analysis populations:**

Patients who took at least 1 dose of damoctocog alfa pegol in the study will be eligible for safety analysis. The full analysis set (FAS) will include all SAF patients who have data on infusions and or bleeding events available. This will include patients who were not followed-up for 3 complete years of prophylaxis. PK analyses will be performed on the PK analysis set. The PK analysis set includes all SAF patients who have evaluable PK data.

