### **9.7.3 Analysis of treatment exposure**

Analysis of treatment exposure will be performed on the SAF.

In this study, the following 4 types of exposure based on physician's prescription will be considered:

- Prophylaxis: twice weekly (including any prescription more than 7 times per month).
- Prophylaxis: every 5 days (including any prescription between >5-7 times per month).
- Other: if not listed above.
- All.

The damoctocog alfa pegol exposure will start with the first infusion in the study. The period of continuous exposure per treatment pattern (following approved local label), stops whenever prescribed damoctocog alfa pegol treatment regimen changes. Treatment patterns for non-naïve patients will also be summarized.

Exposure duration (in days) will be analyzed descriptively by summary statistics and frequency tables per treatment pattern.

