#### **ABR:**

Summary statistics of the number, type, location, and severity of reported bleeds (total, spontaneous, joint, and trauma) will be presented.

The primary analysis on ABR will be performed in patients receiving prophylactic treatment. ABRs will first be characterized using descriptive statistics by calculating mean ( $\pm$  standard deviation [SD]), median, minimum, and maximum. Further, the mean ABRs along with 95% CIs will be estimated using a negative binomial regression model corrected for over-dispersion, and with relevant treatment and disease characteristics as covariates and observed prophylactic treatment period as an offset variable.

When enough data is collected, additional analyses include: 1) comparing the ABR in patients receiving prophylactic treatment with those who are not treated with standard prophylaxis; 2) comparing the ABR in patients receiving damoctocog alfa pegol prophylactic treatment with the ABR prior to the damoctocog alfa pegol treatment.

Further details of the analysis will be described in the SAP.

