**Factor consumption:**

Factor consumption will be analyzed descriptively based on the patient infusion diary, including the annualized number of infusions per patient, annualized total/average dose, and other infusion characteristics. Summary statistics and frequency tables will be provided per treatment pattern, treated bleeds, and other events (e.g., surgeries).

Sensitivity analyses will be performed in case of incomplete patient infusion diary.

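### ABR person-time is not limited to periods in which bleeds were documented, so prophylaxis time without bleed reporting can enter the denominator and lower the primary ABR

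*Protocol*

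**What the plan says.** **Denominator.** The abstract states the rule: "ABRs will be calculated as the number of bleeding events divided by the length (in years) of the treatment regimen". Section 9.7.3 says that "the following 4 types of exposure based on physician's prescription will be considered", and that a period of continuous exposure "stops whenever prescribed damoctocog alfa pegol treatment regimen changes". The regression in section 9.7.4 takes the "observed prophylactic treatment period as an offset variable". The protocol does not define *observed* here.

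**Numerator.** Section 9.1 describes bleeds as "reported in patient infusion diaries or documented by physicians, if patient infusion diary is not available". Section 9.3.2 puts bleeds during the study in the patient diary, with serious, life-threatening and surgery bleeds documented by the physician. A footnote to Table 3 adds that the physician asks about bleeds at every visit. Visits are not scheduled by the protocol.

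**Population.** Section 9.7.1: "The full analysis set (FAS) will include all SAF patients who have data on infusions and or bleeding events available". No minimum period of bleed documentation is required.

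**Incomplete documentation.** Section 9.7.5, under factor consumption, says: "Sensitivity analyses will be performed in case of incomplete patient infusion diary". Section 9.7.4 has no counterpart for ABR. Section 9.9 expects diaries to differ between patients. The checklist in Annex 2 concedes that the outcome depends on diary quality, yet marks sensitivity analyses as not applicable.

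**The concern.** A bleeding rate is sound only if numerator and denominator cover the same time. Here the numerator can grow only while someone is recording bleeds, whereas the denominator, read from the abstract together with section 9.7.3, runs for as long as the regimen does. A patient who keeps a diary for part of the regimen and then stops recording still adds regimen time but no bleeds. In the data, that time looks the same as time without bleeding.

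The error has one direction: it makes the ABR smaller and the product look better. Enrolling more patients does not remove it. It may also differ between countries and regimens if diary use differs, which would disturb the planned stratified results and the comparison with the ABR before damoctocog alfa pegol.

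The two wordings of the time base add a second problem. If *observed* in section 9.7.4 means documented time, the descriptive ABR and the model-based ABR of the same patients use different denominators.

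**Working it through.** **Inputs.** From the protocol: 36 months of planned observation (section 9.1); planning mean ABR 6, dispersion 1, n = 180, half width 0.96, and a previous-trial mean ABR of 4 (section 9.5, Table 4). Assumed, because the protocol gives no figure: the number of undocumented months per affected patient (s) and the share of affected patients (f).

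**Step 1: the plan's own precision.** Negative binomial variance = μ + μ²/θ = 6 + 36/1 = 42. Half width = 1.96 × √(42/n). On the log scale it is half the distance between 6 × exp(±1.96 × √((1/6 + 1)/n)).

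| n | Wald | Log scale | Table 4 |
|---|---|---|---|
| 36 | 2.117 | 2.161 | 2.17 |
| 108 | 1.222 | 1.231 | 1.23 |
| 180 | 0.947 | 0.951 | 0.96 |

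The stated half widths are reproduced closely as expected half widths, with no allowance for undocumented time. The value 0.96 serves below as a yardstick.

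**Step 2: one patient.** If bleeding runs at a constant rate μ, and s of 36 counted months yield no bleed record, the computed ABR is μ × (36 − s)/36.

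| Undocumented months | μ = 6 | μ = 4 | Bias |
|---|---|---|---|
| 3 | 5.5 | 3.67 | -8% |
| 6 | 5.0 | 3.33 | -17% |
| 12 | 4.0 | 2.67 | -33% |
| 24 | 2.0 | 1.33 | -67% |

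**Step 3: the cohort.** The mean of patient ABRs is μ × (1 − f × s/36). At μ = 6:

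| Share f (assumed) | s = 12 | s = 24 | Bias at s = 24 |
|---|---|---|---|
| 5% | 5.90 | 5.80 | -3% |
| 10% | 5.80 | 5.60 | -7% |
| 20% | 5.60 | 5.20 | -13% |
| 30% | 5.40 | 4.80 | -20% |

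**Step 4: against the planned precision.** The downward shift equals 0.96 when f = 0.96/(6 × 24/36) = 24% with 24 undocumented months, or f = 0.96/(6 × 12/36) = 48% with 12. At f = 10% and s = 24 the shift is 0.40, less than half of the half width.

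**Step 5: after the change.** With documented time only, the patient in step 2 has μ × (36 − s)/12 bleeds over (36 − s)/12 years, which returns μ. This holds if bleeding is the same in documented and undocumented time.

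**The case against.** The strongest reply is that the problem is assembled from several places. The abstract does not say that the regimen is the prescribed one; that comes from section 9.7.3, which governs the exposure analysis on the safety set. Section 9.7.4 governs ABR and speaks of an observed period, which can be read as excluding undocumented time. Section 9.2.7 ends observation at loss to follow-up, withdrawal or a switch of therapy. Methods for truncated and missing data are left to the SAP, which is not at hand. All of this is fair, and it makes the bias possible rather than certain. What it does not remove is that the abstract fixes a formula without a documentation condition, that section 9.7.3 is the only definition of regimen periods, and that *observed* qualifies treatment and not bleed reporting.

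Four stronger readings are tempting and not supported:

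- **That silent time of up to 24 months counts as bleed-free by rule.** Section 9.2.7 says "In case no information was obtained from a patient within 24 month since the last data collection time point" the site is to make contact. That sets when a site must act. It does not put those months into person-time, and no passage says which date closes person-time for a lost patient.
- **That physicians record only serious bleeds.** They also document bleeds where there is no diary, and they ask at every visit. This covers patients who attend or return; it does not help with a patient who does neither.
- **That leaving outcomes unimputed turns gaps into zeros.** Section 9.7.1 says only that clinical outcomes are in general not imputed. The zero arises from keeping the time in the denominator.
- **That the 10% dropout in section 9.5 is the affected share.** Those patients are removed (200 to 180) before the effectiveness analysis. The 10% row above is an assumed value only.

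It is also true that documented time is not a neutral choice. If patients record or attend more when they bleed, it overstates the ABR.

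**Conclusion.** The point holds as a defect in the definition of the primary denominator. As written, prophylaxis time without bleed documentation can enter the ABR, and wherever it does it lowers the result. The abstract and section 9.7.4 also word the time base differently and need to be reconciled.

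The per-patient size is exact under a constant bleeding rate: the undocumented fraction of counted time. The cohort size cannot be derived from the protocol; the range of about -3% to -20% rests wholly on the assumed shares of 5% to 30% with 24 undocumented months. Such shifts may stay inside the planned confidence interval, but they are systematic. The change is worth making because it concerns the primary endpoint and is cheap.

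**What to change.** 1. Use one time base in the abstract and in section 9.7.4, for both the descriptive ABR and the offset: prophylaxis time covered by a diary or by physician bleed documentation, including intervals closed by a visit at which bleeds were asked about.
2. For lost patients, end this time at the last documented contact.
3. Report ABR on full regimen time as a sensitivity analysis.
4. Extend the incomplete-diary sensitivity analysis of section 9.7.5 to ABR.

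The 24-month interval before sites follow up a silent patient need not change for this.

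**Cost.** Wording, and a derivation from diary and visit dates that the study already collects. Person-time falls slightly and the confidence interval widens slightly. The main estimate then relies on similar bleeding in documented and undocumented time. The full-time analysis helps to bracket this: it treats undocumented time as bleed-free, so the two results enclose the true rate if bleeding in undocumented time lies between zero and the documented rate.
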